12.6. Appendix 6: Genetics

USE/ANALYSIS OF DNA

- Genetic variation may impact a participant's response to therapy, susceptibility, severity and progression of disease. Variable response to therapy may be due to genetic determinants that impact drug absorption, distribution, metabolism, and excretion; mechanism of action of the drug; disease etiology; and/or molecular subtype of the disease being treated. Therefore, where local regulations and IRB/IEC allow, a blood sample will be collected for DNA analysis.
- DNA samples will be used for research related to nemiralisib or COPD and related diseases. They may also be used to develop tests/assays including diagnostic tests) related to nemiralisib or study treatments of this drug class, and COPD. Genetic research may consist of the analysis of one or more candidate genes (including but not limited to: *PIK3CD*, *PIK3CA*, *IL10*, *CHRNA3*, *CHRNA5*, *DNAH5*, *SUMF1*, and *CELSR1*) or the analysis of genetic markers throughout the genome [or analysis of the entire genome] (as appropriate)
- DNA samples may be analyzed to help understand the clinical data.
- The samples may be analyzed as part of a multi-study assessment of genetic factors involved in the response to nemiralisib or study treatments of this class. The results of genetic analyses may be reported in the clinical study report or in a separate study summary.
- The sponsor will store the DNA samples in a secure storage space with adequate measures to protect confidentiality.
- The samples will be retained while research on nemiralisib (or study treatments of this class) or COPD continues but no longer than 15 years after the last subject last visit or other period as per local requirements.

12.7. Appendix 7: Liver Safety: Required Actions and Follow-up Assessments

12.7.1. Phase II Liver Chemistry Stopping Criteria

Liver Chemistry Stopping Criteria – Liver Stopping Event	
ALT absolute	ALT \geq 5xULN
ALT Increase	ALT \geq 3xULN persists for \geq 4 weeks
Bilirubin ^{1,2}	ALT \geq 3xULN and bilirubin \geq 2xULN (>35% direct bilirubin)
INR ²	ALT \geq 3xULN and INR>1.5, if INR measured
Cannot Monitor	ALT \geq 3xULN and cannot be monitored weekly for 4 weeks
Symptomatic ³	ALT \geq 3xULN associated with symptoms (new or worsening) believed to be related to liver injury or hypersensitivity
Required Actions and Follow up Assessments following ANY Liver Stopping Event	
Actions	Follow Up Assessments

 Immediately discontinue study treatment Report the event to GSK within 24 hours Complete the liver event CRF and complete SAE data collection tool if the event also meets the criteria for an SAE² Perform liver event follow up assessments Monitor the participant until liver chemistries resolve, stabilize, or return to within baseline (see MONITORING below) Do not restart/rechallenge participant with study treatment unless allowed per protocol and GSK Medical Governance approval is granted (refer to Section 8.1.8.1 Section 12.7) If restart/rechallenge not allowed per protocol or not granted, permanently discontinue study treatment and may continue participant in the study for any protocol specified follow up assessments (may include if applicable details on required follow up assessments) 	
 Viral hepatitis serology⁴ Obtain INR and recheck with each liver chemistry assessment until the transaminases values show downward trend Blood sample for pharmacokinetic (PK) analysis, obtained within 14 days after last dose⁵ Serum creatine phosphokinase (CPK) and lactate dehydrogenase (LDH). Fractionate bilirubin, if total bilirubin \geq2xULN Obtain complete blood count with differential to assess eosinophilia Record the appearance or worsening of clinical symptoms of liver injury, or hypersensitivity, on the AE report form Record use of concomitant medications on the concomitant medications report form including acetaminophen, herbal remedies, other over the counter medications. Record alcohol use on the liver event alcohol intake case report form


MONITORING: For bilirubin or INR criteria:
 
 Repeat liver chemistries (include ALT, AST, alkaline phosphatase, bilirubin) and perform liver event follow up assessments within 24 hrs Monitor participants twice weekly until liver chemistries resolve, stabilize or return to within baseline 	
For bilirubin or INR criteria:
 
 Anti-nuclear antibody, anti-smooth muscle antibody, Type 1 anti-liver kidney microsomal antibodies, and quantitative total immunoglobulin G (IgG or gamma globulins). Serum acetaminophen adduct HPLC assay (quantifies
--	--

 • A specialist or hepatology consultation is recommended • For All other criteria: • Repeat liver chemistries (include ALT, AST, alkaline phosphatase, bilirubin) and perform liver event follow up assessments within 24-72 hrs • Monitor participants weekly until liver chemistries resolve, stabilize or return to within baseline 	
potential acetaminophen contribution to liver injury in participants with definite or likely acetaminophen use in the preceding week [James, 2009]). NOTE: not required in China
 
 • Liver imaging (ultrasound, magnetic resonance, or computerised tomography) and /or liver biopsy to evaluate liver disease; complete Liver Imaging and/or Liver Biopsy CRF forms.
---	--

1. Serum bilirubin fractionation should be performed if testing is available. If serum bilirubin fractionation is not immediately available, discontinue study treatment for that participant if ALT $\geq 3 \times \text{ULN}$ and bilirubin $\geq 2 \times \text{ULN}$. Additionally, if serum bilirubin fractionation testing is unavailable, record presence of detectable urinary bilirubin on dipstick, indicating direct bilirubin elevations and suggesting liver injury.
2. All events of ALT $\geq 3 \times \text{ULN}$ and bilirubin $\geq 2 \times \text{ULN}$ (>35% direct bilirubin) or ALT $\geq 3 \times \text{ULN}$ and INR > 1.5, if INR measured which may indicate severe liver injury (possible 'Hy's Law'), must be reported as an SAE (excluding studies of hepatic impairment or cirrhosis); INR measurement is not required and the threshold value stated will not apply to participants receiving anticoagulants
3. New or worsening symptoms believed to be related to liver injury (such as fatigue, nausea, vomiting, right upper quadrant pain or tenderness, or jaundice) or believed to be related to hypersensitivity (such as fever, rash or eosinophilia)
4. Includes: Hepatitis A IgM antibody; Hepatitis B surface antigen and Hepatitis B Core Antibody (IgM); Hepatitis C RNA; Cytomegalovirus IgM antibody; Epstein-Barr viral capsid antigen IgM antibody (or if unavailable, obtain heterophile antibody or monospot testing); Hepatitis E IgM antibody
5. PK sample may not be required for participants known to be receiving placebo or non-GSK comparator treatments.) Record the date/time of the PK blood sample draw and the date/time of the last dose of study treatment prior to blood sample draw on the CRF. If the date or time of the last dose is unclear, provide the participant's best approximation. If the date/time of the last dose cannot be approximated OR a PK sample cannot be collected in the time period indicated above, do not obtain a PK sample. Instructions for sample handling and shipping are in the SRM.

12.7.2. Phase II Liver Chemistry Increased Monitoring Criteria with Continued Therapy

Liver Chemistry Increased Monitoring Criteria – Liver Monitoring Event

Criteria	Actions

ALT \geq3xULN and $<$5xULN and bilirubin $<$2xULN, without symptoms believed to be related to liver injury or hypersensitivity, and who can be monitored weekly for 4 weeks
	
 • Notify the GSK medical monitor within 24 hours of learning of the abnormality to discuss participant safety. • Participant can continue study treatment • Participant must return weekly for repeat liver chemistries (ALT, AST, alkaline phosphatase, bilirubin) until they resolve, stabilise or return to within baseline • If at any time participant meets the liver chemistry stopping criteria, proceed as described above • If, after 4 weeks of monitoring, ALT $<$3xULN and bilirubin $<$2xULN, monitor participants twice monthly until liver chemistries normalize or return to within baseline

12.8. Appendix 8: Medical Device Incidents: Definition and Procedures for Recording, Evaluating, Follow-up, and Reporting

Definition and Documentation of Medical Device Incidents

Definitions of a Medical Device Incident

The detection and documentation procedures described in this protocol apply to all GSK medical devices provided for use in the study (see Section 9.2.9 for the list of GSK medical devices).

Medical Device Incident Definition

 A medical device incident is any malfunction or deterioration in the characteristics and/or performance of a device as well as any inadequacy in the labeling or the instructions for use which, directly or indirectly, might lead to or might have led to the death of a participant/user/other person or to a serious deterioration in his/her state of health.

 Not all incidents lead to death or serious deterioration in health. The nonoccurrence of such a result might have been due to other fortunate circumstances or to the intervention of health care personnel.

It is sufficient that:

- An **incident** associated with a device happened and
- The **incident** was such that, if it occurred again, might lead to death or a serious deterioration in health.

A serious deterioration in state of health can include any of the following:

- Life-threatening illness
- Permanent impairment of body function or permanent damage to body structure
- Condition necessitating medical or surgical intervention to prevent one of the above
- Fetal distress, fetal death, or any congenital abnormality or birth defects

Examples of incidents

- A participant, user, caregiver, or healthcare professional is injured as a result of a medical device failure or its misuse.
- A participant's study treatment is interrupted or compromised by a medical device failure.
- A misdiagnosis due to medical device failure leads to inappropriate treatment.
- A participant's health deteriorates due to medical device failure.

Documenting Medical Device Incidents**Medical Device Incident Documenting**

- Any medical device incident occurring during the study will be documented in the participant's medical records, in accordance with the investigator's normal clinical practice, and on the appropriate form.
- For incidents fulfilling the definition of an AE or an SAE, the appropriate AE/SAE CRF page will be completed as described in [Appendix 4](#).
- The form will be completed as thoroughly as possible and signed by the investigator before transmittal to the GSK.
- It is very important that the investigator provides his/her assessment of causality (relationship to the medical device provided by GSK) at the time of the initial report and describes any corrective or remedial actions taken to prevent recurrence of the incident.
- A remedial action is any action other than routine maintenance or servicing of a medical device where such action is necessary to prevent recurrence of an incident. This includes any amendment to the device design to prevent recurrence.

12.9. Appendix 9: Guidelines for COPD Exacerbation Identification, Categorization, Reporting, and Treatment

12.9.1. Guidelines for Identifying an Acute Exacerbation of COPD

For this protocol, eligible participants must have an acute exacerbation of COPD requiring an escalation in therapy to include oral/systemic corticosteroid(s) **and** antibiotic(s) as defined in Inclusion Criterion 4.

Acute exacerbation is to be confirmed by an experienced physician and to represent a recent worsening in at least two major and one minor symptoms, one major and two minor symptoms, or all 3 major symptoms.

a. Major symptoms:

- i. Subjective increase in dyspnea
- ii. Increase in sputum volume
- iii. Change in sputum color

b. Minor symptoms:

- i. Increased cough
- ii. Increased wheeze
- iii. Sore throat
- iv. Colds (nasal discharge and/or nasal congestion)
- v. Fever (oral temperature >37.5 °C) without other cause

12.9.2. COPD Exacerbation Severity

For the purposes of this study, each COPD exacerbation (including the index exacerbation at Screening and subsequent exacerbation[s]) will be categorized based upon the GOLD [GOLD, 2017] classification of severity as follows:

- **Mild COPD exacerbation:** Worsening symptoms of COPD treated with short-acting bronchodilators (SABDs) only
- **Moderate COPD exacerbation:** worsening symptoms of COPD treated with SABDs plus antibiotics **and/or** oral/systemic corticosteroids
- **Severe COPD exacerbation:** worsening symptoms of COPD that require hospitalization or visit to the emergency room. Severe exacerbation may also be associated with acute respiratory failure.

For this study, mild, moderate and severe exacerbations of COPD will be captured in the eCRF (See Section 12.9.4.).

Note: Use of oral/systemic corticosteroids and antibiotics for the treatment of upper or lower respiratory tract infections will not be considered a COPD exacerbation unless the participant experiences worsening symptoms of COPD, which match the definition of an exacerbation as given above.

12.9.3. Subsequent COPD Exacerbation(s)

After the index exacerbation of COPD at Screening (Visit 1) has resolved, any randomized participant who experiences worsening of COPD for >48 hours should:

- Contact his/her study investigator and/or research coordinator immediately, and report to the study clinic as required
- If the participant is unable to contact his/her study investigator and/or research coordinator, he/she should contact his/her primary care physician (or other health care practitioner as required) and contact their study site as soon as possible
- Continue to complete the eDiary
- If the participant seeks emergent/acute care for worsening respiratory symptoms, he/she should inform the caring Health Care Provider (HCP) to contact the investigator as soon as possible.

Participants with presence of worsening respiratory symptoms will be classified by the Investigator as having:

- A mild/moderate/severe COPD exacerbation and/or pneumonia
- A lower respiratory tract infection (LRTI) [i.e., other than pneumonia]
- Background variability of COPD
- A non-respiratory-related disease
- Other respiratory-related disease

Investigators and site/hospital staff should remain vigilant for the possible development of pneumonia in patients with COPD, as the clinical features of such infections overlap with the symptoms of COPD exacerbations (See Section 12.9.7).

If, based upon these criteria, a participant's symptoms do not fulfil the diagnosis of a COPD exacerbation and/or pneumonia, then the investigator should use his/her clinical judgment to assess the participant's symptoms (including increased volume of sputum production and/or change in the sputum color) for a diagnosis of LRTI (e.g., acute bronchitis), background variability of COPD, a non-respiratory-related disease or other

respiratory-related disease. Investigator judgment should be used in deciding whether to report the signs and symptoms (and/or determined diagnosis) as an AE/SAE in the eCRF.

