9.2. Adverse Events

The definitions of an AE or SAE can be found in [Appendix 4](#).

The investigator and any designees are responsible for detecting, documenting, and reporting events that meet the definition of an AE or SAE and remain responsible for following up AEs that are serious, considered related to the study treatment or the study, or that caused the participant to discontinue the study treatment or study (see Section 8).

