9.2.1. Time Period and Frequency for Collecting AE and SAE Information

- All SAEs will be collected from the start of study treatment until Visit 9 in the Post-Treatment Follow-Up Period, at the time points specified in the SoA (Section 2). However, any SAEs assessed as related to study participation (e.g., study intervention, protocol-mandated procedures, invasive tests, or change in existing therapy) or related to a GSK product will be recorded from the time a subject consents to participate in the study.
- All AEs will be collected from the start of double-blind study treatment until Visit 9 in the Post-Treatment Follow-Up Period at the time points specified in the SoA (Section 2).
- Medical occurrences that begin before the start of study treatment but after obtaining informed consent will be recorded on the Medical History/Current Medical Conditions section of the eCRF not the AE section.
- All SAEs will be recorded and reported to the sponsor or designee as soon as possible and not more than 24 hours, as indicated in [Appendix 4](#). The investigator will submit any updated SAE data to the sponsor within 24 hours of it being available.
- Investigators are not obligated to actively seek AEs or SAEs in former study participants. However, if the investigator learns of any SAE, including a death, at any time after a participant has been discharged from the study, and he/she considers the event to be reasonably related to the study treatment or study participation, the investigator must promptly notify the sponsor.
- The method of recording, evaluating, and assessing causality of AEs and SAEs and the procedures for completing and transmitting SAE reports are provided in [Appendix 4](#).

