- Source documents provide evidence for the existence of the participant and substantiate the integrity of the data collected. Source documents are filed at the investigator's site.
- Data reported on the CRF or entered in the eCRF that are transcribed from source documents must be consistent with the source documents or the discrepancies must be explained. The investigator may need to request previous medical records or transfer records, depending on the study. Also, current medical records must be available.
- Definition of what constitutes source data can be found in the Source Document Agreement (SDA).

Study and Site Closure

GSK or its designee reserves the right to close the study site or terminate the study at any time for any reason at the sole discretion of GSK. Study sites will be closed upon study completion. A study site is considered closed when all required documents and study supplies have been collected and a study-site closure visit has been performed.

The investigator may initiate study-site closure at any time, provided there is reasonable cause and sufficient notice is given in advance of the intended termination.

Reasons for the early closure of a study site by the sponsor or investigator may include but are not limited to:

- Failure of the investigator to comply with the protocol, the requirements of the IRB/IEC or local health authorities, the sponsor's procedures, or GCP guidelines
- Inadequate recruitment of participants by the investigator
- Discontinuation of further study treatment development

12.4. Appendix 4: Adverse Events: Definitions and Procedures for Recording, Evaluating, Follow-up, and Reporting

Definition of AE

AE Definition

- An AE is any untoward medical occurrence in a clinical study participant, temporally associated with the use of a study treatment, whether or not considered related to the study treatment.
- NOTE: An AE can therefore be any unfavorable and unintended sign (including an abnormal laboratory finding), symptom, or disease (new or exacerbated) temporally associated with the use of a study treatment.

Events Meeting the AE Definition

- Any abnormal laboratory test results (hematology, clinical chemistry, or urinalysis) or other safety assessments (eg, ECG, radiological scans, vital signs measurements), including those that worsen from baseline, considered clinically significant in the medical and scientific judgment of the investigator (ie, not related to progression of underlying disease).

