12.9.7. Pneumonia

Participants who develop pneumonia during the 12-Week Double-Blind Treatment Period should discontinue study treatment.

For the purpose of this study, pneumonia is defined as new auscultatory findings compatible with parenchymal lung infection and/or radiographic evidence of parenchymal/air space disease. All suspected cases of pneumonia are encouraged to be confirmed radiographically within 48 hours of diagnosis. All diagnoses of pneumonia (radiographically confirmed or unconfirmed) must be reported as an AE or SAE (if applicable). Information regarding chest X-ray-confirmed cases of pneumonia will be recorded in the eCRF. Details regarding the information to be captured for pneumonias will be provided in the SRM.

All medications used to treat the pneumonia are to be recorded in the source documentation and in the eCRF.

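### Section 12.9.3 leaves AE reporting of a diagnosed respiratory infection to the investigator, against the protocol's own AE rules

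*Protocol*

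**What the plan says.** Section 12.9.3 governs respiratory worsening after the index exacerbation has resolved. The investigator classifies each episode. The part at issue opens only when a participant's "symptoms do not fulfil the diagnosis of a COPD exacerbation and/or pneumonia". The remaining options are then an LRTI (acute bronchitis is the example given), background variability of COPD, a non-respiratory disease or another respiratory disease. The paragraph ends: "Investigator judgment should be used in deciding whether to report the signs and symptoms (and/or determined diagnosis) as an AE/SAE in the eCRF".

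The general safety sections read differently. Section 9.2 says that the investigator and designees "are responsible for detecting, documenting, and reporting events that meet the definition of an AE or SAE". Section 9.2.1 says: "All AEs will be collected from the start of double-blind study treatment until Visit 9 in the Post-Treatment Follow-Up Period". Appendix 4 (Section 12.4) begins: "An AE is any untoward medical occurrence in a clinical study participant, temporally associated with the use of a study treatment". It lists conditions newly detected or diagnosed after dosing among the events that qualify. Its exemption covers the disease under study and that disease's expected course and symptoms.

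Two neighbouring rules in Appendix 9 matter as well. Under Section 12.9.2, steroids and antibiotics given for a respiratory tract infection "will not be considered a COPD exacerbation unless the participant experiences worsening symptoms of COPD, which match the definition of an exacerbation". For pneumonia, Section 12.9.7 leaves no choice: "All diagnoses of pneumonia (radiographically confirmed or unconfirmed) must be reported as an AE or SAE (if applicable".

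**The concern.** Section 12.9.3 is the specific instruction for respiratory worsening, so it is the one a site will have open when such an episode occurs. It makes the reporting of a determined diagnosis a matter of judgment, while the general sections make it a duty. An infection in this branch is by construction not an exacerbation, so the exacerbation form does not pick it up. If the investigator also decides against an AE entry, neither of the two main data sets contains it.

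Respiratory infection is not incidental in this trial. Section 3.2 describes the target as a kinase expressed mainly in leukocytes and presents control of bacterial infection as part of the rationale. AE incidence is a secondary endpoint (Section 4). The internal Safety Review Committee may recommend changes to treatment allocation from interim safety data (Section 7.2 and Appendix 3). Capture that depends on each site's reading of one sentence weakens the infection counts used for both purposes.

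**Working it through.** No arithmetic applies. The protocol gives no LRTI rate, no expected reporting fraction and no planned test on LRTIs. The check is to follow one event through the rules.

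**The event.** A randomized participant on study treatment develops acute bronchitis and receives antibiotics. The investigator judges that neither the exacerbation definition nor the pneumonia definition is met.

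1. *Exacerbation form.* Section 12.9.2 does not count treatment for a respiratory infection as an exacerbation unless COPD symptoms worsen and match the definition. Here they do not, so there is no entry.
2. *Pneumonia rule.* Section 12.9.7 makes pneumonia reportable in all cases. This event is not pneumonia, so that rule does not reach it. Appendix 9 has no equivalent sentence for LRTI.
3. *AE form under Section 12.9.3 read alone.* The diagnosis has been made, and the closing sentence names the determined diagnosis as something the investigator may or may not report. The same sentence covers SAEs. An entry is possible but not required.
4. *AE form under Sections 9.2, 9.2.1 and Appendix 4.* The event is an untoward occurrence during treatment and a newly diagnosed condition. Appendix 4 exempts COPD and its expected symptoms; it does not name an LRTI that the investigator has separated from COPD. An entry is required.

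Steps 3 and 4 give different answers for the same event, and nothing in 12.9.3 says which section governs. Under the first answer the event is in neither the exacerbation data nor the AE data.

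**Where judgment does fit.** The same sentence also covers background variability of COPD. Discretion there agrees with the Appendix 4 exemption for the disease under study. The conflict is confined to episodes that end in a diagnosis other than COPD.

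**How clear the boundary is.** Section 12.9.3 names more sputum and a change in its color as features to weigh when considering an LRTI. Section 12.9.1 lists both among its three major exacerbation symptoms. Similar presentations can therefore take either label, which makes it more useful to have the LRTI label recorded consistently.

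**What is still recorded.** Section 7.7 requires every medication with its dates and reason for use. Section 9.1.3.1 collects daily diary answers on sputum color, wheeze, sore throat, colds and fever. Section 9.4.5 has participants enter medical problems in the eDiary for review at visits, with transfer to the AE page where appropriate. Section 9.10 puts details of unscheduled health-care contacts for any cause into the eCRF. None of these is an AE record with intensity, causality and outcome.

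**The case against.** The best defense is that Section 12.9.3 does not claim to override the general rules. Its closing sentence can be read as telling the investigator to apply the Appendix 4 definition across a mixed list, one item of which properly calls for judgment. On that reading Sections 9.2 and 9.2.1 still bind and nothing is lost. The reading is possible, and it limits how serious the point is. It does not remove the point, because the sentence expressly includes a determined diagnosis and refers to no definition or other section. Two careful sites could follow it differently.

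Three stronger readings are tempting, and the documents do not support them.

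- *That treated LRTIs are kept out of the exacerbation count altogether.* The exclusion in 12.9.2 is conditional. A treated infection with COPD worsening that matches the definition is counted as an exacerbation. Only infections below that definition are affected.
- *That a missed LRTI leaves no trace.* The medication, eDiary and health-care-contact records listed above would usually show one.
- *That the wording biases the key secondary comparison or costs a calculable amount of safety power.* Whether an LRTI is entered as an AE does not change the number of exacerbations. A shift in the rate ratio would need investigators to label events differently by arm, and they are blinded (Section 7.4). Any power figure would rest on invented incidences and attach to no planned test, since Section 10.3.2 provides for summaries of safety endpoints by treatment group.

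**Conclusion.** The contradiction stands, and it is minor. Section 12.9.3 makes reporting of a diagnosed LRTI, or of another non-COPD diagnosis, discretionary where Sections 9.2 and 9.2.1 and Appendix 4 make it mandatory. Followed as written, it allows such an event to be absent from both the exacerbation and the AE data, with uneven capture between sites. The practical effect depends on how many LRTIs fall short of the exacerbation definition and on how many sites use the discretion. The documents give neither figure, so no size is claimed. The conclusion rests on two readings of the text: that the closing sentence of 12.9.3 means what it says about a determined diagnosis, and that an LRTI distinguished from COPD lies outside the Appendix 4 exemption. The absence of a sensitivity analysis that counts treated LRTIs is not part of the point, because such detail may sit in the analysis plan, which is not shown.

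**What to change.** Replace the closing sentence of Section 12.9.3 so that it agrees with Section 9.2.1 and Appendix 4. It should state that any diagnosed LRTI, other respiratory disease or non-respiratory disease not recorded as an exacerbation is reported as an AE, or as an SAE if serious, when it meets the Appendix 4 definition. Investigator judgment should be kept only for symptoms attributed to background variability of COPD.

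The cost is one sentence in Appendix 9, a note to sites and a few more AE entries. No endpoint, visit or analysis changes.
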